6.1.1 Relevant physical, chemical and pharmaceutical properties

The product is provided as a concentrate; the drug product for supply of clinical trials is a vial with 30 mg temsirolimus concentrate in 1.2 ml. Because addition to aqueous solutions leads to precipitation of the product, the concentrate should be diluted in the supplied diluent only.

6.1.2 Instructions for storage and handling

The vial containing the temsirolimus concentrate should be stored under refrigeration at 2-8°C and be protected from light. The concentrate may only be used until the expiration date provided on the vial.

For intravenous infusion, the concentrate has to be attenuated in 1.8 ml supplied diluent leading to a concentration of 10 mg study medication or placebo per ml. The concentrate-diluent mixture is stable for 24h at controlled room temperature. The intended dose will rapidly be added to 250 ml 0.9% sodium chloride. Administration of study medication must be completed within 6h after final dilution in the 250 ml 0.9% sodium chloride.

During preparation and administration, study drug should be light-protected. As the solution is not compatible with PVC-containing infusion material (temsirolimus concentrate contains polysorbate 80) the sodium chloride injection container should be of non-DEHP-containing materials (glass, polyolefin, polyethylene or polypropylene). Visual inspection for particulate matter and discoloration has to be performed prior to administration.

The solution has to be administered by 30-60 minute infusion.

For further information please refer to the 'Fachinformation Deutschland'.

6.1.3 Interactions with concomitant medications

Pharmacokinetic studies about the interaction between temsirolimus and other drugs inducting or inhibiting CYP-enzymes have been performed.

As temsirolimus can be metabolized by the CYP3A4 isoenzyme, strong CYP3A4 inducers may reduce exposure to the major metabolite of temsirolimus and should be avoided. If patients must be co-administered a strong CYP3A4 inducer, based on pharmacokinetic studies, a temsirolimus dose increase should be considered, such as from 25 mg/week up to 50 mg/week, as long as the inducer is administered. Strong CYP3A4 inducers include but are not limited to dexamethasone, phenytoin, carbamazepine, phenobarbital, rifampin, rifabutin, rifampacin, and St. John's Wort (for a complete list see website below).

Strong CYP3A4 inhibitors may increase blood concentrations of the major metabolite of temsirolimus and should be avoided. If patients must be co-administered a strong CYP3A4 inhibitor, based on pharmacokinetic studies, a temsirolimus dose reduction should be considered, such as from 25 mg/week down to 12.5 mg/week. If the strong inhibitor is discontinued, a washout period of approximately 1 week should be allowed before the temsirolimus dose is adjusted back to the dose used prior to initiation of the strong CYP3A4 inhibitor. Strong CYP3A4 inhibitors include but are not limited to ketoconazole, itraconazole, clarithromycin, atazanavir, indinavir, nefazodone, nelfinavir, ritonavir, saquinavir, telithromycin, and voriconazole. Grapefruit juice may also increase plasma concentrations of sirolimus (a major metabolite of temsirolimus) and should be avoided.

A list of strong CYP3A4 inducers and inhibitors is available at: http://medicine.iupui.edu/flockhart

6.1.4 Drug accountability

The study's active drug (temsirolimus) will be distributed to the center pharmacies by the central pharmacy of this study.

The center pharmacy is responsible for ordering more supply at least three working days ahead of time.

For the active drug each center pharmacy has to keep a drug accountability log provided by the sponsor. The placebo drug (250 ml 0.9% NaCl) is provided by the center pharmacies. In order to maintain the double-blind character of the study, the center pharmacies will always label both the prepared active drug and the placebo in the same fashion before delivering them to the medical ward (label includes Patient name, Patient ID, study code TOR-AML, and dose level in mg).

The person applying the study medication has to document the drug application and - in case of a failure to administer the medication - a short statement, why medication was not applied, in a patient record.

6.2 Standard cytotoxic therapy

Chemotherapy is administered according to general standards defined by national and international expert groups. All drugs are approved. Therefore the standard cytotoxic treatment is NOT an investigational product in this study. All statements regarding dosage and timing of the standard chemotherapy are recommendations based on long-standing experience with this therapy. In the best interest of the patient individual deviations from the schedule are possible and sometimes required particularly in the target population of this trial, which are older patients.

Supportive care of the patients will be conducted according to general standards of care for acute leukemia patients and is not part of this trial.

6.2.1 Cytarabine (AraC)

For all drug information on cytarabine (AraC) please refer to the "Fachinformationsverzeichnis Deutschland" in its latest version.

6.2.2 Daunorubicin

For all drug information on daunorubicin please refer to the "Fachinformationsverzeichnis Deutschland" in its latest version.

6.2.3 Mitoxantrone

For all drug information on mitoxantrone please refer to the "Fachinformationsverzeichnis Deutschland" in its latest version.

6.2.4 Overlapping toxicities of temsirolimus and standard cytotoxic therapy

Potential overlapping toxicities of temsirolimus and standard cytotoxic therapy include:

- Increased severity and duration of hematological toxicity, including anemia, thrombocytopenia and leukopenia
- Increased risk or severity of nephrotoxicity

• Further non-hematological overlapping toxicities cannot be ruled out

6.2.5 Dose reduction in standard cytotoxic therapy

In principle, dose reduction of standard cytotoxic therapy is not permitted in this study – with the exception of individual cases in the best interest of the patient. In case that overlapping toxicities of standard cytotoxic treatment and temsirolimus should require a dose reduction, the dose of temsirolimus must be reduced (for dose modification and delay see 6.3.3).

If individual cases of severe toxicities should require an additional dose reduction of standard cytotoxic therapy, the coordinating investigator should first be consulted, if possible, before dose reduction. Dose reduction and reason for dose reduction should be documented. Depending on the toxicities and dose modification, the patient might be withdrawn from the study.

6.3 Treatment

6.3.1 Run-in part: Dose finding for temsirolimus

In order to address the toxicity profile of temsirolimus added to induction chemotherapy, a **run-in part** with 12 (to 18) patients will be conducted. Patients in this part of the study will be randomized between dose level 1 (12.5mg, n=6) and dose level 2 (25mg, n=6). The optimal dose-level will be determined after 1-2 induction cycles.

After the run-in part, the study will be on hold until the decision by the Data Safety Monitoring Board on dose finding is completed, which may include an additional 6 patients at previously tested or additional dose levels or schedules.

All toxicity during induction therapy will be graded according to the Common Toxicity Criteria for Adverse Events v. 4.0 (CTCAE).

DLT in the run-in part of the trial is defined as:

- CTCAE Grade 4 neutropenia (ANC <0.5 x 109/L) lasting ≥ day 42 after last chemotherapy
- \circ CTCAE Grade 4 thrombocytopenia (platelets < 25 x 109/L) lasting \geq day 42 after last chemotherapy
- CTCAE Grade 3 non-hematologic temsirolimus-related adverse events (excluding hypertension and nausea / vomiting which is not medically managed)

Patients must be evaluable for DLT assessment. Patients with early death during induction due to events unrelated to temsirolimus treatment e.g. infection will not be considered as DLT. Patients with neutropenia or thrombocytopenia due to refractory or recurrent AML will not be considered for DLT. If such cases occur additional evaluable patients will be included.

If < 2 out of 6 patients experience DLT at dose level 2 during induction chemotherapy, dose level 2 will be chosen for temsirolimus during the main part. If > 2 of 6 patients experience DLT at dose level 2 and < 2 out of 6 patients experience DLT at dose level 1, then dose levels 1 will be chosen for temsirolimus during the main part. If 2 out of 6 patients experience DLT at dose level 2 and \leq 2 patients experience DLT at dose level 1, the Data Safety Monitoring Board (DSMB) may opt to include additional 6 patients in dose level 2 of the run-in phase.

Depending on the results, the DSMB may consider an additional dose level to be tested in 6 additional patients or terminate the trial.

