4.2 Benefit / risk ratio

Patients eligible for this trial have a risk of treatment failure with standard chemotherapy of 70-80% at two years. Treatment failure is not compatible with long-term survival in these elderly patients. Included in these numbers are disease-related events (refractory disease, relapse) and treatment-related mortality that has to be expected to reach up to 10% in this patient group. The risk of this trial is that addition of temsirolimus to the standard treatment increases treatment-related mortality due to higher toxicity. Therefore the optimal temsirolimus dose level will be tested in the run-in part of this study, which will precede the randomized main part.

The possible benefit of the trial is to decrease the rate of treatment failure in the trial population. For a single patient, this could result in increased life-span, ideally without evidence of leukemia. Given the extensively high rate of treatment failure and the high toxicity of the currently available standard therapy, the medical need for novel, rational therapeutic approaches for this patient population is overwhelming. As pointed out above, the molecular rationale for the therapeutic administration of temsirolimus in AML is well founded. Thus, the Benefit/Risk ratio for a patient to participate in this trial seems very favorable.

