8.12.1.2 List of adverse drug reactions

As reported in the summary of product characteristics for 25mg temsirolimus i.v. (mostly from clinical information on renal cell carcinoma patients):

System organ category	Preferred term	Frequency
very common >10% -100%; com	nmon >1% -10%; uncommon >0.1%-1%	; rare < 0,1%
Infections and infestations	bacterial and viral infection (incl. infection, cellulutis, bronchitis, sinusitis, herpes zoster, herpes simplex)	very common
	upper respiratory tract infection	very common
	urinary tract infection (incl. dysuria, urinary frequency, urinary tract infection, urinary urgency)	very common
	pharyngitis	very common
	pneumonia (incl. interstitial pneumonia)	very common
	rhinitis	common
	folliculitis	common
	sepsis (incl. sepsis, septic shock)	common
Blood and lymphatic system disorders	thrombocytopenia	very common
	anemia	very common
	neutropenia	very common
	leukopenia	very common
	lymphocytopenia	very common
Immune system disorders	allergic/hypersensitivity reactions	common
Metabolism and nutrition disorders	hypokalaemia	very common
	anorexia	very common
	hyperglycemia/diabetes mellitus	very common
	hypercholesterolaemia	very common
	hyperlipaemia	common
	dehydration	common
	hypocalcaemia	common
	hypophosphataemia	common
Psychiatric disorders	insomnia	very common
	anxiety	very common
	depression	common
Nervous system disorders	dysgeusia	very common
	ageusia	common
	dizziness	common
	paraesthesia	common

Eye disorders	conjunctivitis	common
	eye haemorrhage	common
Vascular disorders	thrombosis (incl. deep venous thrombosis, thrombosis)	common
	hypertension	common
Respiratory, thoracic and mediastinal disorders	dyspnea	very common
	epistaxis	very common
	cough	very common
	pneumonitis	common
Gastrointestinal disorders	diarrhea	very common
	nausea	very common
	vomiting	very common
	stomatitis (incl. aphtous stomatitis, mouth ulceration, stomatitis, glossitis, oral pain))	very common
	abdominal pain	very common
	gingivitis	common
	dysphagia	common
	bowel perforation	common
	gastrointestinal haemorrhage (incl. gastrointestinal haemorrhage, rectal haemorrhage)	common
	gingivitis	common
	gastritis	common
Skin and subcutaneous tissue disorders	rash	very common
	pruritus	very common
	nail disorders	very common
	dry skin	very common
	acne	common
	moniliasis	common
	fungal dermatitis	common
	ecchymosis	common
Musculoskeletal and connective tissue disorders	arthralgia	very common
	back pain	very common

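### The run-in DLT definition names only grade 3 for non-hematologic events and cites infection as its example of an unrelated death, although treatment-related mortality is the stated reason for the run-in

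*Protocol*

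**What the plan says.** Protocol 4.2 names the risk: "The risk of this trial is that addition of temsirolimus to the standard treatment increases treatment-related mortality due to higher toxicity". It then draws the consequence: "Therefore the optimal temsirolimus dose level will be tested in the run-in part of this study, which will precede the randomized main part".

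Section 6.3.1 defines DLT in three parts, and the synopsis repeats them:

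- The neutropenia criterion is "CTCAE Grade 4 neutropenia (ANC <0.5 x 109/L) lasting ≥ day 42 after last chemotherapy". The thrombocytopenia criterion has the same form.
- The non-hematologic criterion is "CTCAE Grade 3 non-hematologic temsirolimus-related adverse events (excluding hypertension and nausea / vomiting which is not medically managed").
- On deaths: "Patients with early death during induction due to events unrelated to temsirolimus treatment e.g. infection will not be considered as DLT". After this exclusion and a second one, for cytopenia caused by leukemia, the text says: "If such cases occur additional evaluable patients will be included".

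The dose rule follows: "If < 2 out of 6 patients experience DLT at dose level 2 during induction chemotherapy, dose level 2 will be chosen" for the main part.

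Other sections bear on the same events:

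- 6.3.3.3 and the matching synopsis table name grades 3 and 4 together for dose modification.
- 8.12.1.1 puts bacterial and viral infections among reactions seen in more than 10% and up to 30% of patients. 8.12.1.2 lists such infections and pneumonia as very common, and "sepsis (incl. sepsis, septic shock") as common.
- 8.2 says CTCAE grade 5 is not used, 8.4 has fatal as a severity category, and 8.7 asks for grades 1 to 5 on SAE reports.

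**The concern.** The outcome that justifies the run-in is not clearly inside the quantity that decides the dose. Taken at its word, the definition leaves out a temsirolimus-related grade 4 non-hematologic event and a temsirolimus-related death. Where the protocol means two grades it elsewhere writes both, so a reader cannot safely assume that grade 3 here stands for grade 3 or higher.

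The infection example adds to this. Attribution of a fatal infection during induction is difficult, because chemotherapy and temsirolimus can both contribute; 6.2.4 itself lists more severe and longer leukopenia as a possible overlapping toxicity. Offering infection as the one example of an unrelated event points the investigator to one answer before the case is examined. A patient so classified then also leaves the denominator through replacement. The run-in has no group without temsirolimus against which a misattribution would show. At stake is the dose given to the temsirolimus arm of a 200-patient trial.

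**Working it through.** **1. Which early events can count, on the literal text**

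| Event in induction | Hematologic criteria | Non-hematologic criterion |
|---|---|---|
| Related, grade 3 | no | yes |
| Related, grade 4 | no | not named |
| Related, fatal, before day 42 | cannot be met | not named; 8.2 does not use grade 5 |
| Fatal infection judged unrelated | cannot be met | excluded, patient replaced |

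**2. Inputs for an illustration**

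The protocol gives no target DLT rate and no operating characteristics for the run-in, so there is no figure to reproduce.

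- Rule (6.3.1): dose level 2 is chosen outright with 0 or 1 DLT in 6.
- Early non-leukemic mortality m: 4.2 expects treatment-related mortality of up to 10% with standard therapy. I use m = 10% for early deaths; 20% is an assumption.
- Rate r of other DLTs: 10% is an assumption, with 0 and 20% as the range. Independence of r and m is also assumed.

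**3. Formulas**

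P(dose level 2 chosen) = (1−q)^6 + 6q(1−q)^5, where q is the counted DLT rate.

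- Deaths attributed to infection and replaced: q = r.
- All such deaths counted: q = 1 − (1−r)(1−m).

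**4. Results for r = 10%**

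- Not counted: q = 0.10, so 0.9^6 + 6(0.1)(0.9^5) = 0.531 + 0.354 = 0.89. The value does not contain m, so it is the same at any early mortality.
- Counted, m = 10%: q = 1 − 0.9 × 0.9 = 0.19, giving 0.68.
- Counted, m = 20%: q = 1 − 0.9 × 0.8 = 0.28, giving 0.46.

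| r | Not counted, any m | Counted, m = 10% | Counted, m = 20% |
|---|---|---|---|
| 0 | 1.00 | 0.89 | 0.66 |
| 10% | 0.89 | 0.68 | 0.46 |
| 20% | 0.66 | 0.46 | 0.30 |

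**5. How often the question would arise**

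The chance of at least one such death among 6 patients is 1 − 0.9^6 = 0.47 at m = 10% and 1 − 0.8^6 = 0.74 at m = 20%. These are chances that an attribution must be made, not chances of a wrong dose.

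**The case against.** The strongest reply is that the count does not act alone. The study is on hold after the run-in until the DSMB has decided (4.4, 6.3.1). The DSMB may ask for another dose level or end the trial (6.3.1), may decide on a dose other than 25 mg (6.3.2), and shares the final choice (11.1). This stands, and it rules out the inference that the DLT count by itself fixes the dose. It does not repair the text: the sentence for fewer than two DLTs is unconditional, and no mortality criterion is written for the run-in.

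A reader might also infer that no infection death can ever count. The documents do not say so. The exclusion is limited to deaths judged unrelated, and 8.5 and 11.1 give the DSMB the final say where the investigator records a possible relation. That route opens only once the investigator has recorded it, which the example discourages.

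Nor are deaths hidden. Under 8.5 death is an SAE criterion, except when clearly due to leukemia progression, and 8.7 requires a report within 24 hours. What is missing is a set presentation by dose level before the decision.

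Counting every early death is not a neutral correction either. The 10% in 4.2 is expected without temsirolimus. With no drug toxicity at all, the chance of two or more such deaths in 6 is 1 − 0.886 = 0.11, so chemotherapy deaths alone would sometimes block dose level 2. In addition, 4.2 gives an upper figure for all treatment-related deaths, not for induction or infection deaths, and the frequencies in 8.12.1.2 come mostly from renal cell carcinoma.

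Two smaller points stand. Section 6.3.3.3 serves individual dose modification, so it shows how the protocol writes grades but does not itself define DLT. And the nausea and vomiting clause is ambiguous, not demonstrably reversed.

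**Conclusion.** The concern holds as a contradiction between the DLT definition and the protocol's own purpose and safety text. Section 6.3.1 and the synopsis do not settle whether non-hematologic events above grade 3 are DLTs. They use as the example of an unrelated death a kind of event that the protocol lists as a temsirolimus reaction, and three sections disagree on how a death is graded.

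Read literally, and with early deaths attributed to infection, the dose level 2 rule is insensitive to early mortality: 0.89 at any mortality, against 0.68 and 0.46 at 10% and 20% if all such deaths counted. Those figures rest on an assumed 10% rate of other DLTs, independence, and application of the 4.2 mortality figure to induction. They show how the rule responds; they do not estimate the chance of a wrong dose. Because of the DSMB's role, the supported conclusion is that the dose can be chosen without counting these deaths, not that it must be.

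**What to change.** Reconcile 6.3.1 and the synopsis with 4.2, 6.3.3.3, 8.2, 8.4, 8.7, 8.12.1.1 and 8.12.1.2, so that:

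1. the text states unambiguously whether non-hematologic events above grade 3 are within the DLT count;
2. infection is no longer presented as unrelated by example, and attribution follows the DSMB process in 8.5 and 11.1;
3. one convention for grading death applies throughout.

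In addition, tabulate all induction deaths by dose level, including those of replaced patients, for the DSMB before its dose decision. The nausea and vomiting clause can be clarified in the same amendment.

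What the criterion should contain clinically is for the sponsor and the DSMB to settle. The cost is amendment wording and one table, with no added procedures.

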3 BACKGROUND INFORMATION / INTRODUCTION

In acute myeloid leukemia (AML) treatment failure and relapse are frequently observed despite intensive chemotherapy and allogeneic bone marrow transplantation, leading to a cure in less than 30% of adults with AML [1]. Prognostic factors include age over 60 years, cytogenetics and molecular aberrations such as mutations in Flt3 (Flt3-ITD) and NPM. In patients over 60 years induction chemotherapy with cytarabine and an anthracycline (such as daunorubicin or mitoxantrone) leads to complete remission in only approximately 50% [2]. Consolidation therapy following the induction of an initial complete response is essential to prevent relapse. Three options are generally available: allogeneic or autologous bone marrow transplantation or chemotherapy. Transplantation is more often used in young patients with adverse karyotypes and chemotherapy in good prognosis or elderly patients [2]. Nontransplant consolidation chemotherapy regimens commonly contain cytarabine. While consolidation therapy following the induction is essential to maintain complete remission, relapse frequently occurs leading to a long-term disease-free survival in 10% to 20% [2].

AML is a clonal, malignant disorder that results from genetic and epigenetic changes in pluripotent stem or slightly more differentiated progenitor cells. The aberrant cells gain a growth and/or survival advantage in relationship to the normal pool of stem cells. The most common genetic aberrations seen in acute myeloid leukemia (AML) are oncogenic K-RAS and N-RAS-mutations as well as activating mutations of the receptor tyrosine kinase Flt3 (Flt3-ITD). Both oncogenic RAS and Flt3-ITD, as well as other receptor tyrosine kinases activated in AML (such as cKIT and PDGFRβ), activate the phosphatidylinositol 3-Kinase (PI3K) / AKT pathway in myeloid cells, which regulates proliferation and apoptosis in myeloid leukemia cells [3]. As a result, AKT was found to be activated in 86% of AML patients [3], which leads to the activation of mTOR in AML [4].

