5 SELECTION, RANDOMIZATION AND WITHDRAWAL OF PATIENTS

5.1 Number of patients

For the run-in part, accrual of 12 (up to 18) patients is planned (see chapter 6.3.1). According to the power calculations given in section 9.1, n = 200 patients will be included in the main (controlled) part of the study with an equal allocation rate to both treatment arms.

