	day 42 after last chemotherapy • CTCAE Grade 3 non-hematologic temsirolimus-related adverse event (excluding hypertension and nausea / vomiting which is not medically managed) Patients must be evaluable for DLT assessment. Patients with early death during induction due to events unrelated to temsirolimus treatment e.g infection will not be considered as DLT. Patients with neutropenia of thrombocytopenia due to refractory or recurrent AML will not be considered for DLT. If such cases occur additional evaluable patients will be included.		
	If < 2 out of 6 patients experience DLT at dose level 2 during induction chemotherapy, dose level 2 will be chosen for temsirolimus during the main part. If > 2 of 6 patients experience DLT at dose level 2 and < 2 out of 6 patients experience DLT at dose levels 1 will be chosen for temsirolimus during the main part. If 2 out of 6 patients experience DLT at dose level 2 and \leq 2 patients experience DLT at dose level 1, the Data Safety Monitoring Board (DSMB) may opt to include additional 6 patients in dose level 2 of the run-in phase. Depending on the results, the DSMB may consider an additional dose level to		
	be tested in 6 additional patients or terminate the trial. Main part A total of 146 evaluable patients are expected to be sufficient to detect a prolongation of the median EFS from 7 to 11.75 months with a power of 80% and a significance level of α =0.05. Under the assumption of loss to follow-up or of alternate post-remission treatment (i.e. bone marrow transplantation), or protocol violation in up to 54 patients, total accrual to the phase II part of this trial is planned for 200 patients (100 per arm).		
Sample size	Run-in-part: A maximum of evaluable 18 patients will be enrolled Main part: 200 patients will be enrolled (100 in each treatment group)		
Trial duration	- First patient in: - Last patient in: - Last patient in: - Recruitment: - Treatment: - Follow up: - Trial duration: - End of study: January 2nd, 2014 - 2014 - January 2nd, 2014 - January 2nd, 2014 - January 2nd, 2014 - January 2nd, 2016		

Performance Status

ECOG		Karnofsky	
Score	Description	Score	Description
disease performance without	Fully active, able to carry on all predisease performance without restriction.	100	Normal, no complaints, no evidence of disease.
		90	Able to carry on normal activity; minor signs or symptoms of disease.

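### Run-in patients with AML-related cytopenia are taken out of DLT assessment altogether and replaced, so a temsirolimus-related non-haematologic DLT in such a patient is not counted in the dose decision

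*Protocol*

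**What the plan says.** Section 6.3.1 defines three kinds of DLT in the run-in: grade 4 neutropenia persisting to day 42 or beyond after the last chemotherapy, grade 4 thrombocytopenia persisting equally long, and grade 3 non-haematologic events related to temsirolimus (with stated exceptions). It then says "Patients with neutropenia or thrombocytopenia due to refractory or recurrent AML will not be considered for DLT", followed by "If such cases occur additional evaluable patients will be included". The synopsis repeats both sentences.

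The decision rule uses six patients per level. Fewer than 2 of 6 with DLT at dose level 2 selects that level for the main part. Exactly 2, or more than 2, leads to other branches that also use these counts.

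On size, patients are "randomized between dose level 1 (12.5mg, n=6) and dose level 2 (25mg, n=6"). The DSMB decision may add a further group, "which may include an additional 6 patients at previously tested or additional dose levels or schedules". Section 6.3.1 says "a run-in part with 12 (to 18) patients will be conducted". Section 5.1 says "For the run-in part, accrual of 12 (up to 18) patients is planned". The sample size row of the synopsis says "A maximum of evaluable 18 patients will be enrolled".

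**The concern.** The reason given for the exclusion is that the low counts come from the leukaemia and not from the drug. That justifies leaving the two haematologic criteria unscored. It says nothing about, for example, a related grade 3 pneumonitis in the same patient. Yet the sentence has the patient as its subject, and the next sentence brings in a further evaluable patient. Nothing in the protocol returns that patient's non-haematologic event to the count.

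The patients affected matter for the question the run-in asks. Section 6.3.1.3 gives the second induction to patients with partial remission or treatment failure on the day 15 marrow. Section 6.3.1.4 gives temsirolimus on two further days of that cycle, with high-dose cytarabine and mitoxantrone. A patient still refractory after that has had four temsirolimus infusions instead of two. Section 6.2.4 says that overlapping non-haematologic toxicity beyond the listed items is possible. The dose for a main part of 200 patients would then rest on a count that leaves out related toxicity in some of the most heavily exposed patients.

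**Working it through.** **1. Scope of the exclusion.** Setting the reason against each criterion:

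| DLT criterion | Does AML-related cytopenia explain it away? | Counted as the text stands? |
|---|---|---|
| Prolonged grade 4 neutropenia | Yes | No |
| Prolonged grade 4 thrombocytopenia | Yes | No |
| Grade 3 non-haematologic, temsirolimus-related | No | No |

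The third row is the defect.

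**2. Effect on the decision rule.** The protocol gives neither DLT risks nor the share of patients excluded, so these are assumptions. Let q be the share excluded, p_k the DLT risk in kept patients and p_x the risk of a countable DLT in excluded patients. Only non-haematologic events can count in the latter.

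- As written, the risk per counted patient is p_k.
- If everyone counted, it is p = (1 − q)p_k + q·p_x.
- The chance that dose level 2 passes is P(X < 2 of 6) = (1 − p)^6 + 6p(1 − p)^5.

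As written with p_k = 0.20: 0.262 + 0.393 = 0.655.

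| q | p_k | p_x | p, all counted | As written | All counted |
|---|---|---|---|---|---|
| 0.40 | 0.20 | 0.20 | 0.20 | 0.655 | 0.655 |
| 0.20 | 0.20 | 0.40 | 0.24 | 0.655 | 0.558 |
| 0.40 | 0.20 | 0.40 | 0.28 | 0.655 | 0.464 |

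The direction can also reverse. Take 10% haematologic and 10% non-haematologic risk, independent, so p_k = 1 − 0.9 × 0.9 = 0.19, with q = 0.40. If p_x is 0.10, then p = 0.6 × 0.19 + 0.4 × 0.10 = 0.154, and the pass probability moves from 0.68 to 0.77. If p_x is 0.20, then p = 0.194 and it moves from 0.68 to 0.67. Pooling every patient into the 2-of-6 rule is therefore not a safe remedy: patients scored on one criterion out of three dilute the count.

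**3. A rule that keeps six patients per level.** Suppose an excluded-type patient with a non-haematologic DLT counts and stays among the six, and only those without a DLT are replaced. The risk per counted patient becomes [(1 − q)p_k + q·p_x] / [(1 − q) + q·p_x]. With p_k = 0.19 and p_x = 0.10:

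- q = 0.10: 0.181 / 0.91 = 0.199, pass probability 0.66 (as written 0.68).
- q = 0.20: 0.172 / 0.82 = 0.210, pass probability 0.63.
- q = 0.40: 0.154 / 0.64 = 0.241, pass probability 0.56.

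This rule is conservative: slightly when exclusions are few, more clearly when they are many.

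**4. The run-in size.** The stated figures reproduce as 6 + 6 = 12 and 6 + 6 + 6 = 18. The last six are the optional DSMB group, so neither figure contains an allowance for replacements. If 18 is a limit on accrual, the chance that 18 enrolled yield at least 12 evaluable patients is P(Bin(18, 1 − q) ≥ 12): 0.95 at q = 0.20, 0.72 at 0.30 and 0.37 at 0.40. If 18 counts evaluable patients, there is no conflict, and enrolment is larger. On average, 12 evaluable patients then need 12 / (1 − q) enrolled: 15 at q = 0.20 and 20 at q = 0.40.

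**The case against.** **The sentence may be loosely worded.** The sentence before it says that patients with an unrelated early death are not considered as DLT, where an event is plainly meant. The disputed sentence may likewise mean only that leukaemic cytopenia is not a DLT. That is possible, but the replacement sentence points the other way: a patient still assessable on the third criterion would not simply be replaced. A DLT count should not depend on which reading is chosen.

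**The safety data are not lost.** Section 8.2 has adverse events of all grades recorded in the run-in, the trial is on hold until the DSMB has decided, and section 11.1 involves the DSMB in the final dose. All of this is true and limits the harm. It does not put the event back into the count on which section 6.3.1 says dose level 2 will be chosen.

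**Two stronger readings are tempting, and the documents do not support them.**

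- A reader might infer that the run-in size cannot fit the protocol's own remission rate, since section 3 says induction over age 60 "leads to complete remission in only approximately 50"%. That is a background figure, not a planning assumption for the run-in. Patients without CR also include those with CRi or a leukaemia-free state, early deaths (section 4.2 expects treatment-related mortality of up to 10%) and non-responders without AML-related cytopenia. Half is therefore only an upper bound on exclusions. Section 6.3.1 also sets no cap on replacements, and the synopsis counts evaluable patients.
- A reader might also infer that the dose would be chosen mainly on good responders with the least exposure. Patients who need the second induction and then clear their leukaemia stay evaluable, with all four infusions. Two-cycle toxicity is thinned, not discarded.

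**Conclusion.** The concern holds for the scope of the exclusion. On its literal wording, section 6.3.1 and the synopsis drop a related non-haematologic DLT from the dose decision for a reason that has nothing to do with that event. This follows from the text and needs no assumption about rates.

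The size of the effect cannot be stated from the protocol. It is nil when the risk is the same in kept and excluded patients. The drop from 0.66 to 0.46 rests on a doubled risk in excluded patients, all of it non-haematologic, and on 40% being excluded. None of these is a document figure. The run-in is meant to learn whether toxicity differs in these patients, and the rule as written prevents the DLT count from showing it.

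On size, what stands is narrower: section 5.1 and the synopsis disagree on whether 18 counts accrued or evaluable patients, and neither 12 nor 18 has room for replacements. This should be corrected before the run-in starts, but it does not invalidate the design.

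**What to change.** In section 6.3.1 and the synopsis, replace the exclusion sentence with wording to this effect: cytopenia due to refractory or recurrent AML is not scored as a haematologic DLT; a non-haematologic DLT in such a patient counts as a DLT and the patient stays among the six for that level; only such patients without a DLT are replaced. This keeps the 2-of-6 rule defined on six patients.

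Give the DSMB, beside that count, the number of non-haematologic DLTs over all treated patients at each level. This shows the rate without the effect of replacement.

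State once, in the same words in sections 4.4, 5.1 and 6.3.1 and in the synopsis, whether 12 and 18 are enrolled or evaluable patients, and how many replacements are allowed for.

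The cost is a few sentences and one small DSMB table. No new data are needed, because run-in adverse events of all grades are already recorded. The downside is that replacing only patients without a DLT makes the rule conservative. In the illustration above, the pass probability falls from 0.68 to 0.66 with 10% excluded and to 0.56 with 40%. The all-treated table lets the DSMB see how far this matters.
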